Cognitive remediation (CR) is a psychological intervention based on principles of learning and neuroplasticity to improve neurocognitive abilities with the ultimate goal of improving community functioning. The neuroplastic effects of CR are well established with evidence for increased gray matter volume in the hippocampus and amygdala,^[5] increased activation of the medial prefrontal cortex,^[6] and increased amplitude of the mismatch negativity event-related potential^[7] following CR. In two recent randomized controlled trials (RCTs), I also demonstrated that CR improves synchronization of neural networks in the alpha and theta frequency bands.^[7,8] Meta-analyses support moderate transfer of these neurophysiological improvements to neurocognitive abilities ($d = 0.45$) and community functioning ($d = 0.37$).^[9] In a recent systematic review, I reported that CR approaches vary widely, but approaches that incorporate training of executive functions are generally the most effective.^[10] Based on these findings **I developed a novel CR intervention specifically targeting executive functions** and conducted two double-blind RCTs, in which targeted executive function training (ET) produced greater improvements in neurophysiology, neurocognition, functional skills and real-world community functioning compared to other leading forms of CR.^[7,8] This intervention is approximately half the duration of other CR programs, yet produces larger effect size improvements in community functioning.

Justification for Research

In order to further increase the efficiency and effectiveness of ET it is necessary to determine the active component of treatment. There are two primary components of ET and neither have ever been examined in isolation: 1) computerized cognitive training, and 2) strategy development. It is unclear whether both components are necessary to stimulate neurophysiological changes and improve functioning or whether one component drives the observed treatment effects. Dismantling ET will provide critical information regarding whether a single component is necessary or whether it is the interaction of these components that results in effective CR.

This will be the first study to dismantle CR and examine components necessary to effectively improve neurocognition and functioning for individuals with schizophrenia. These findings will directly inform methods of improving CR efficacy.

Purpose and Hypotheses

The primary goal of this study is to:

- (1) Examine the efficacy of computerized training alone, compared to strategy monitoring alone, compared to full ET on neurocognition, and functioning.

STUDY DESIGN

Sample Size/Subject Selection

90 participants with schizophrenia-spectrum disorders will be recruited.

Inclusion Criteria

The target population for this study are those who meet the criteria for schizophrenia based on the DSM-V diagnosis. The inclusion criteria is anyone who meets the criteria of schizophrenia, schizoaffective disorder or any other psychotic disorder, are also 18-65 years of age, know how to use a computer, are not abusing drugs or alcohol and can read and speak English.

Exclusion Criteria

Exclusion criteria include anyone enrolled in a cognitive training program in the last 6 months, anyone with a neurological disease or neurological damage, medical illnesses that can change neurocognitive function, medical history of head injury with loss of consciousness and those with physical handicaps.

Method of Recruitment

The participants will be recruited from various sources including mental health agencies and referrals from mental health providers.

Limitation of the study

The primary limitation of the study will be attrition if participants do not complete the study or the follow-up assessment.

Informed Consent

A consent form will be given to all participants to sign. The language of the consent form will be written at an elementary school level. A research assistant will read out the consent form to participants and will clarify anything and answer any participant questions. They will also ask the participant questions during the consenting process to ensure that the participant understands. Participants will also be reminded that it is their right to refuse to participate or withdraw from the study and that doing so will not affect their existing treatments or services.

STUDY PROCEDURE

Randomization

Participants will be randomized to receive Computerized Cognitive Training only, Strategy Development only, or both (ET).

Study Intervention/Standard of Care

All interventions will involve 4 weeks of group treatment consisting of two 1-hour group sessions per week and additional practice at home between sessions. The **Executive Training** condition will consist of the ET intervention that I previously developed and evaluated.^[7] ET sessions consist of 50% of the session practicing computerized cognitive training exercises, and 50% of the session developing cognitive strategies to use in the computerized exercises. Participants are encouraged to complete 40 minutes of computerized training per day, and complete strategy worksheets, at home between sessions. In **Computerized Cognitive Training only** participants will spend the entire one-hour session practicing computerized training exercises. Between sessions participants will be encouraged to practice the computerized exercises at home for 40 minutes per day. There will be no strategy development in this condition. In **Strategy Development only** participants will engage in cognitive strategy discussions to develop new executive function strategies that can be used in daily life. Between sessions, participants will be encouraged to practice their cognitive strategies in their daily life and track their strategies using the strategy worksheet. There will be no computerized cognitive training in this condition. All interventions will be delivered virtually in the participant's home and group sessions will be conducted using the online platform Zoom.

Outcome Measures

The primary outcome measure is community functioning measured using the Specific Levels of Functioning scale which will be rated by a participant's case manager who is familiar with their everyday activities and independent from the trial. I have successfully used this method of objectively measuring functioning in several previous studies.^[7,8]

The secondary outcome measures include the Cambridge Neuropsychological Test Automated Battery (CANTAB), the Virtual Reality Functional Capacity Assessment Tool (VRFCAT), the Wide Range Achievement Test (WRAT), the Questionnaire About the Process of Recovery (QPR), the Brief Psychiatric Rating Scale (BPRS), the Quality of Life Enjoyment and Satisfaction Questionnaire (Q-LES-Q), the Dysfunctional Attitudes Scale (DAS), the Brief Core Schema Scale (BCSS), the Generalized Self-Efficacy Scale (GSES), the Cognitive Failures Questionnaire (CFQ), the Need for Cognition Scale (NCS), the Davos Assessment of Cognitive Biases (DACOBS), and the Motivation and Pleasure Scale - Self-Report (MAP-SR).^[11-23]

The CANTAB is a battery consisting of highly sensitive, precise and objective measures of cognitive function. It includes tests of working memory, learning and executive function; visual, verbal and episodic memory; attention, information processing and reaction time; social and emotion recognition, decision making and response control. The VRFCAT is a measure of functional capacity that simulates activities of daily living in a virtual environment and improves clinical trials by detecting functionally meaningful improvements in patients' everyday lives. The WRAT is an academic skills assessment which measures reading skills, math skills, spelling, and comprehension. The QPR was developed from service users' accounts of recovery from psychosis in collaboration with local service users. It asks people living with psychosis about aspects of recovery that are meaningful to them, and is strongly associated with general psychological wellbeing, quality of life and empowerment. The BPRS measures psychopathology and symptom severity and is sensitive to changes in symptom levels. The Q-LES-Q is a sensitive measure of the degree of enjoyment and satisfaction experienced by subjects in various areas of daily functioning. The DAS measures self-

defeating attitudes theorized to underlie clinical depression and anxiety. The BCSS assesses four dimensions of self and other evaluation: negative-self, positive-self, negative-other, and positive-other. The GSES assesses optimistic self-beliefs to cope with a variety of difficult demands in life. The CFQ was designed to measure perception, memory, and motor lapses in daily life. The NCS measures "the tendency for an individual to engage in and enjoy thinking." The DAVOS measures cognitive biases and discriminates between schizophrenia spectrum patients and normal control subjects. The MAP-SR assesses the motivation and pleasure domains of negative symptoms.

Visits and Rationale

Visits: All interventions will involve 4 weeks of group treatment consisting of two 1-hour group sessions per week and additional practice at home between sessions.

Rationale: In order to further increase the efficiency and effectiveness of ET it is necessary to determine the active component of treatment. It is unclear whether both components are necessary to stimulate neurophysiological changes and improve functioning or whether one component drives the observed treatment effects. Dismantling ET will provide critical information regarding whether a single component is necessary or whether it is the interaction of these components that results in effective CR. Therefore, the proposed number and length of sessions are justifiable because the proposed number and length of sessions are congruent with ET and will allow the present research questions to be addressed.

Data Collection, Storage, Privacy, Destruction

Privacy: Information provided will not have any identifying features on it. A random code will be assigned to each participant and those numbers will be used to refer to a participant's data. The document linking names to codes will be kept in [name] locked laboratory on a password protected computer.

Limits to Confidentiality: Limitations that will require confidentiality to be broken include: if a research member is aware of child abuse where the child might still be a risk, if a participant expresses that they are risk of harming themselves or others, and if a participant expresses that another health professional has engaged in sexual abuse.

Data Storage: All de-identified forms will be kept in a locked cabinet where only members of the research team have access to it. Information kept on a computer will be password protected. All filing cabinets and computers will be located in [name] locked laboratory that only research staff have access to. All research staff receive data protection and confidentiality training and sign a confidentiality form.

Data Retention/Destruction: De-identified data will be kept for seven years before being destroyed. Only members of [name] lab will have access to the data.

STUDY ANALYSIS

Sample size Statistics

90 participants with schizophrenia-spectrum disorders will be recruited. Power analyses, conducted with GPower, indicate that 90 participants (30 per treatment condition), accounting for an upper limit of 25% attrition observed in my previous trials of ET,^[7,8] provides 80% power to detect a medium effect size (Cohen's $f = 0.2$) difference between conditions.

Statistical Plan

Primary and secondary outcomes will be examined using Linear Mixed Models on the Intent-to-Treat sample with missing data interpolated using maximum likelihood estimation. The primary endpoint is the 3-month follow-up assessment, and secondary endpoint of post-treatment will also be examined.

STUDY ETHICS

Potential Benefits

The direct benefit to the participant includes improvements in attention, memory and problem solving, caused by the treatment. Also, if the results are released to the participant's clinical treatment team, they can use it to help with the ongoing care. There is also a potential benefit to the scientific community because the results may help in understanding individual differences.

Potential Risks

Psychological/emotional risks may arise during assessment procedures due to frustration or embarrassment during the neurocognitive assessment trials. Participants may feel uncomfortable discussing personal topics related to their symptoms or they may become tired. These risks are equal to those that occur within the clinical context. Participants will be reminded that they are able to stop the interview at any time to take a break or to postpone the procedure to a different day. Participants will also be given the phone number of a mental health professional if discomfort does occur.

Safety Provisions

All therapists and lab staff will be trained in suicide risk assessment procedures. Therapists will follow established protocols to conduct a risk assessment if there is any indication of suicide risk. Therapists will create a safety plan with the participant if risk is low or moderate. If risk is high, then therapists will collaboratively discuss the risk with the participant and escort participants to the emergency department at the respective hospital site (CAMH, Ontario Shores, or Scarborough Health Network). If a risk assessment is required during an assessment, one of the assessors will conduct an initial assessment with the participant. If risk is above minimal, assessor will immediately consult with [name] on the best course of action before continuing the assessment. If risk is determined to be high then the participant will be collaboratively escorted to the emergency department.

During the consenting process participants will be asked comprehension questions about the consent form to ensure participants are aware of what they are consenting to.

Ethics Approval

This protocol is currently under review at the University of Toronto Research Ethics Board. Approval from the University of Toronto REB will be forwarded to Ontario Shores Centre for Mental Health Sciences upon approval.

Dissemination

Results from this research will be presented at academic conferences and submitted for publication at peer-reviewed journals.

Statement of Right to withdraw from the study

Participants can withdraw from the study at any time. If participants decide that they would like to withdraw their data from the study, then their data will be destroyed.

REFERENCES

- [1] Wu, E. Q. et al. The Economic Burden of Schizophrenia in the United States in 2002. *J. Clin. Psychiatry* 66, 1122–1129 (2005).
- [2] Palmer, B. A., Pankratz, V. S. & Bostwick, J. M. The Lifetime Risk of Suicide in Schizophrenia: A Reexamination. *Arch Gen Psychiatry* 62, 247–253 (2005).
- [3] Eack, S. M. & Newhill, C. E. Psychiatric Symptoms and Quality of Life in Schizophrenia: A Meta-Analysis. *Schizophr. Bull.* 33, 1225–1237 (2007).
- [4] Swartz, M. et al. Effects of Antipsychotic Medications on Psychosocial Functioning in Patients with Chronic Schizophrenia: Findings from the NIMH CATIE Study. *Am J Psychiatry* 164, 428–436 (2007).

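### The rationale promises to say whether the components interact, but with no arm lacking both components the trial can only compare three programmes as delivered

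*Combined protocol and SAP*

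**What the plan says.** All references are to the combined protocol and SAP.

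- **Justification for Research**, repeated in **Visits and Rationale**: the question is posed as "It is unclear whether both components are necessary to stimulate neurophysiological changes and improve functioning or whether one component drives the observed treatment effects", and the study is said to provide information on "whether a single component is necessary or whether it is the interaction of these components that results in effective CR".
- **Purpose and Hypotheses**: the goal is narrower and comparative: "Examine the efficacy of computerized training alone, compared to strategy monitoring alone, compared to full ET on neurocognition, and functioning".
- **Randomization**: three arms, namely computerized training only, strategy development only, or both (ET). No arm has neither component.
- **Study Intervention/Standard of Care**: ET splits each session evenly between computer exercises and strategies for use in those exercises. Training-only spends the whole hour on the exercises. Strategy-only develops strategies for daily life.
- **Limitation of the study**: "The primary limitation of the study will be attrition if participants do not complete the study or the follow-up assessment". Nothing is said about a reference arm.
- **Sample size Statistics**: 90 participants, 30 per arm, with up to 25% attrition, which "provides 80% power to detect a medium effect size (Cohen's $f = 0.2$) difference between conditions".
- **Statistical Plan**: linear mixed models on the intent-to-treat sample, with the primary endpoint at 3 months. There is no interaction contrast, and no statement of how pairwise differences will be reported or a null result read.

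**The concern.** The rationale asks more than the arms can answer, in two ways.

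First, an interaction is a statement about four conditions, and the trial observes three. If ET beat both single arms, the present wording would invite a report of interaction, which the data could not support. If all three arms changed equally, the trial could not say whether all were effective or none was.

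Second, the other answer on offer, that one component drives the effect, would come from seeing no difference between ET and that component. The plan is powered to detect a difference and does not say what the absence of a significant one would mean. A component might then be judged dispensable on a p-value alone, although the protocol intends the findings to guide how cognitive remediation is improved.

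**Working it through.** **1. Estimability.** Code each arm as (1, training, strategy, product):

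- training only (1, 1, 0, 0)
- strategy only (1, 0, 1, 0)
- both (1, 1, 1, 1)

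The rank is 3 for 4 parameters. Adding a neither arm (1, 0, 0, 0) gives rank 4. Only ET − training, ET − strategy and training − strategy are estimable. The interaction is

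ET − training − strategy + neither.

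Take hypothetical changes of 0.2 (training), 0.2 (strategy) and 0.4 SD (ET). The interaction is 0.4 − 0.2 − 0.2 + neither, that is 0, +0.2 or −0.2 SD if the unobserved change is 0, +0.2 or −0.2 SD. Sample size does not enter.

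**2. Are the pairwise contrasts pure add-one-component contrasts?** No. ET has 50% of the in-session computer time of training-only, and its strategies are aimed at the exercises, whereas strategy-only aims at daily life. Dose and content change along with the presence of a component.

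**3. The plan's own sample size.** The test family, alpha, number of measurements and correlation are not stated. A group-by-time test with 3 groups, f = 0.2, alpha 0.05, 2 measurements and correlation 0.5 (all but f and the groups assumed) needs N = 66, and 66/0.75 = 88, close to 90. Power at 67.5 completers is 0.83. A one-way comparison at f = 0.2 would need 246.

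Under the reading that comes close, the noncentrality is f² × N × 2/(1 − 0.5) = 0.16N, so the effect size on change is √0.16 = 0.4. If one arm differs from two equal arms, d = 0.4 × 3/√2 = 0.85 SD.

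**4. Precision of a pairwise 3-month difference.** SE = √[(2/n)(1 − r²)] in SD units, with 2n − 2 degrees of freedom, two-sided 5%, no multiplicity adjustment. Here n = 22.5 (30 × 0.75) and n = 30 bracket a mixed model that keeps partial data. The baseline correlation r is an assumption. Example: n = 22.5, r = 0 gives SE = √(2/22.5) = 0.298 and half-width 2.017 × 0.298 = 0.601.

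| n per arm | r | 95% CI half-width (SD) | Non-significant if true difference is 0.37 | CI excludes 0.37 if arms equal |
|---|---|---|---|---|
| 22.5 | 0 | 0.601 | 77% | 23% |
| 22.5 | 0.5 | 0.521 | 71% | 29% |
| 22.5 | 0.7 | 0.429 | 60% | 40% |
| 30 | 0 | 0.517 | 71% | 29% |
| 30 | 0.5 | 0.448 | 63% | 37% |
| 30 | 0.7 | 0.369 | 50% | 51% |

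The 0.37 is the community-functioning effect that the background section cites for cognitive remediation generally. It is used for scale. The documents give no expected ET versus single-component difference.

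**5. The same check at 0.85 SD.** At n = 22.5 and r = 0, 0.5, 0.7, a true difference of 0.85 SD would be missed 20%, 10% and 3% of the time. With equal arms, the interval would exclude 0.85 SD 80%, 90% and 97% of the time.

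**The case against.** **Interaction may be meant loosely.** The word appears only in the rationale. The goal is comparative and no interaction contrast is planned. The preceding sentence suggests the sense is whether the combination is needed, which ET beating both single arms would address. This largely stands: no planned analysis is wrong. But even on that reading the result concerns programmes as delivered, and the text still says "whether it is the interaction of these components that results in effective CR".

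**Effectiveness is taken from earlier trials.** The background cites randomised trials in which ET outperformed other forms of cognitive remediation, and a dismantling design without an untreated arm is legitimate. This supports ET only. The protocol says that neither component has been examined alone.

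**Attrition is called the primary limitation, not the only one.** True, but this one bears directly on the stated question.

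Three stronger inferences are tempting and are not supported.

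- *Every non-significant ET versus single-component result is inconclusive.* That depends on the interval. With equal arms it would exclude 0.37 SD in 23% to 51% of trials, and 0.85 SD in most.
- *A fourth arm would isolate the interaction.* It would make the factorial contrast estimable, but dose and content would still differ between arms.
- *The trial intends to report a null as sufficiency, or an ET win as synergy.* The documents do not say so. They leave both readings open.

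**Conclusion.** The concern holds in a limited form. The factorial interaction, and change common to all arms as distinct from time or practice effects, cannot be estimated from these three arms. That follows from the design and rests on no numerical assumption. The comparative goal under Purpose and Hypotheses is sound.

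On reading a null, non-significance alone would not show that one component is enough. With half-widths from 0.60 down to 0.37 SD over the range examined, a difference near 0.37 SD often could not be ruled out, while one near 0.85 SD usually could. These figures assume a baseline correlation of 0 to 0.7 and 22.5 to 30 analysed per arm. The 0.85 SD also assumes the group-by-time reading of f = 0.2, two measurements with correlation 0.5, and one arm differing from two equal arms.

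This should be corrected before results are known. It does not invalidate the trial. A minor related point: the rationale also names neurophysiological changes, which none of the listed outcomes measures.

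**What to change.** 1. **Justification for Research** and **Visits and Rationale**: replace the interaction claim with a pairwise comparison of the three programmes as delivered, matching the stated goal.
2. **Limitation of the study**: add that interaction, and time or practice effects common to all arms, cannot be separated out with these arms, and that component dose and content differ between arms.
3. **Statistical Plan**: report each of the three pairwise 3-month differences from the mixed model with its 95% CI. State that any conclusion that one component is enough will rest on that interval and not on non-significance.
4. Minor: remove neurophysiological changes from the stated question.

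The cost is wording in four sections and three intervals from a model already planned. No new arm or participants are needed. The downside is a more modest claim.

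### The 80% power for f = 0.2 is worded as a difference between conditions, but no test, inputs or scale for f are given, and at the 3-month primary endpoint the sentence overstates the trial's sensitivity

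*Combined protocol and SAP*

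**What the plan says.** Under Study Analysis, Sample size Statistics, the power analyses "indicate that 90 participants (30 per treatment condition), accounting for an upper limit of 25% attrition" seen in earlier trials of the intervention. The conclusion is that this "provides 80% power to detect a medium effect size (Cohen's $f = 0.2$) difference between conditions". GPower is named as the software, but not which of its procedures was used.

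The Statistical Plan, directly below, fixes the time point: "The primary endpoint is the 3-month follow-up assessment, and secondary endpoint of post-treatment will also be examined". It also names the analysis: "Primary and secondary outcomes will be examined using Linear Mixed Models on the Intent-to-Treat sample with missing data interpolated using maximum likelihood estimation". It specifies no fixed effects, baseline covariate or contrast.

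Alpha, the number of measurements, the correlation among them, and whether f refers to an endpoint difference or to a condition-by-time interaction appear nowhere in the document.

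**The concern.** With a single primary time point, a reader will take a between-condition difference of f = 0.2 to be the difference among the three arms at 3 months. For three arms of 30, that effect is small relative to the sample unless baseline explains much of the outcome variance. The same f entered in GPower as a group-by-time interaction is a different and larger quantity at follow-up, and the sentence does not say which was used.

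This matters because the trial compares three active conditions. The Justification for Research says: "Dismantling ET will provide critical information regarding whether a single component is necessary or whether it is the interaction of these components". A non-significant result is a possible outcome, and its meaning depends on which 3-month difference the trial could have detected. If the power statement is taken at face value when it does not apply to the 3-month comparison, a null result could be over-read as showing that the components do not differ.

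**Working it through.** **Inputs from the document:** three arms, 30 each, N = 90; attrition up to 25%, so 90 × 0.75 = 67.5 with 3-month data; f = 0.2; power 80%; primary endpoint at 3 months.

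**Assumptions:** alpha 0.05; all correlations; two or three measurements. Power is from the noncentral F distribution.

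**1. Reproducing the plan's figure.** GPower's within-between interaction has λ = N·m·f²/(1 − ρ), with df 2(m − 1) and (N − 3)(m − 1), where m is the number of measurements.

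With m = 2, ρ = 0.5 and N = 66: λ = 66 × 2 × 0.04/0.5 = 10.56, df 2 and 63, power 0.818. Then 66/0.75 = 88 randomised, against 90 stated. Other inputs give:

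| m | ρ | Analysed for 80% | Randomised | Power at 67.5 |
|---|---|---|---|---|
| 2 | 0.4 | 78 | 104 | 0.75 |
| 2 | 0.5 | 66 | 88 | 0.83 |
| 2 | 0.6 | 54 | 72 | 0.905 |
| 3 | 0.3 | 75 | 100 | 0.77 |
| 3 | 0.4 | 63 | 84 | 0.84 |
| 3 | 0.5 | 54 | 72 | 0.904 |

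At 66–68 analysed, this route reaches 80% once ρ is about 0.46–0.48 (m = 2) or 0.34–0.36 (m = 3).

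GPower's between-factors test, λ = N·m·f²/(1 + (m − 1)ρ), does not reach 80% at 66–68 analysed for ρ from 0 to 0.8; its highest value is 0.705 (m = 3, ρ = 0). With all 90 it reaches 0.83 only at m = 3 and ρ = 0. It tests the average over time points, not 3 months.

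**2. f = 0.2 as the 3-month difference.**
- Unadjusted: λ = N·f², df 2 and N − 3. This gives 67.5 × 0.04 = 2.7 and 90 × 0.04 = 3.6.
- Baseline-adjusted: λ = N·f²/(1 − r²), df 2 and N − 4, where r is the baseline-to-3-month correlation. For example, r = 0.8 gives 2.7/0.36 = 7.5 and 3.6/0.36 = 10.0.

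| | Power, 67.5 analysed | Power, 90 analysed |
|---|---|---|
| Unadjusted | 28% | 37% |
| r = 0.5 | 36% | 47% |
| r = 0.7 | 51% | 64% |
| r = 0.8 | 67% | 80% |
| r needed for 80% | 0.856 | 0.800 |

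**3. Allowing for the planned mixed model.** I took an unstructured covariance, a common baseline mean, 25% missing at 3 months only, and 64 denominator df. Power at r = 0.5, 0.7 and 0.8 is 37%, 53% and 69% if the post-treatment-to-3-month correlation equals r. It is 44%, 59% and 73% if that correlation is 0.9. At r = 0.85 it is 81–83%. These values fall between, or close to, the two columns above.

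**4. Putting the interaction f on the 3-month scale.** With two measurements and equal baselines, each arm's deviation at follow-up splits into halves of opposite sign, so the interaction SD is half the follow-up SD: f at 3 months = 0.2 × 2 = 0.4. With three measurements it depends on the course of the effect: 0.42–0.49 if it persists or grows to 3 months, 0.35 if it falls by a quarter after treatment, and about 0.24 if it halves.

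**5. Effect detectable at 3 months with 80% power.**

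| | 90 analysed | 67 analysed |
|---|---|---|
| Unadjusted | 0.33 | 0.39 |
| r = 0.5 | 0.29 | 0.34 |
| r = 0.7 | 0.24 | 0.28 |
| r = 0.8 | 0.20 | 0.23 |

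**The case against.** The strongest reply is that no arithmetic error has been shown. The power sentence does not itself mention 3 months, and a standard GPower option gives 88 against the stated 90. On that option a correlation above 0.5 yields more than 80%, so the sensitivity to inputs does not all run against the plan. This stands. A reader might infer that the 80% is simply wrong, or out of reach unless the baseline correlation is 0.80 or more. The document does not support that: the threshold applies only if f = 0.2 is the 3-month difference.

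It is also fair that 25% is given as an upper limit, that maximum likelihood uses partial data, and that no correlation for the functioning scale is reported, so a value above 0.8 cannot be ruled out. For that reason the figures are shown from 67.5 to 90 analysed and across correlations.

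What the reply does not remove is the mismatch. If the interaction was the source, f = 0.2 is not the 3-month difference that the sentence appears to describe. If it was not, 80% rests on a high correlation that is nowhere stated.

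**Conclusion.** The point holds as a defect in the power statement. The inputs given do not determine the 80%, and as worded the sentence overstates sensitivity at the primary endpoint.

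If f = 0.2 is the 3-month difference, power is 28–37% unadjusted. It reaches 80% only with a baseline correlation of about 0.80–0.86. If it is a two-measurement interaction with equal baselines, the matching 3-month effect is about 0.4, twice what the sentence suggests.

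These sizes rest on alpha 0.05, the 2-df omnibus test and the assumed correlations. They do not describe pairwise arm comparisons, which need their own calculation.

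Two further inferences are not supported. The interaction calculation is a plausible origin for N = 90, not a documented one. Nor does any of this show that 90 is too few: the document commits to no target 3-month difference on a defined scale against which to judge it.

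**What to change.** In Sample size Statistics, state the GPower procedure, alpha, number of measurements, correlation and the scale of f. Then restate power for the 3-month comparison, for example:

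> With 90 randomised and up to 25% attrition, the 2-df omnibus test of condition at 3 months (alpha 0.05) has 80% power for f of about 0.33–0.39 unadjusted (90 to 67 analysed), or about 0.29–0.34, 0.24–0.28 or 0.20–0.23 adjusted for baseline if the baseline-to-3-month correlation is 0.5, 0.7 or 0.8.

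Replace the assumed correlations with an observed one if it is available. On the case-manager rating, Outcome Measures says "I have successfully used this method of objectively measuring functioning in several previous studies", so the investigator may hold the value. If the 80% was computed for the interaction, say so and give the 3-month effect it corresponds to, with the assumed course of the effect.

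The cost is wording only; enrolment is unchanged. The downside is a less favourable stated figure.
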